 - To assess the association between nutritional status (measured by serum albumin levels) and femoral approach-related SSI up to 28 (± 2) days after surgery.
 - To assess the association between Body Mass Index (BMI) and femoral approach-related SSI up to 28 (± 2) days after surgery.
 - To assess the association between incision length and femoral approach-related SSI up to 28 (± 2) days after surgery.
 - To assess the association between surgery duration and femoral approach-related SSI up to 28 (± 2) days after surgery.
 - To assess the association between the kind of surgery performed and femoral approach-related SSI up to 28 (± 2) days after surgery.
 - To assess the association between length of hospital stay before surgery and femoral approach-related SSI up to 28 (± 2) days after surgery.
 - To assess the association between foot lesions (Rutherford ischemic stages 5 or 6) and femoral approach-related SSI up to 28 (± 2) days after surgery.
 - To estimate the SSI incidence (superficial and/or deep) associated with the femoral approach up to 84 (± 7) days after surgery.

DESIGN

- **STUDY SETTING**

We present a pragmatic, multicenter, randomised clinical trial, approved by the Research Ethics Committee of the Bellvitge University Hospital (PR047/22) and registered on clinicaltrials.gov (NCT05434182). It will be performed in the Bellvitge University Hospital, Germans Trias i Pujol University Hospital, and Trieste University Hospital. These are all specialised healthcare centers with all the means necessary to carry out complex surgeries.

- **ELEGIBILITY CRITERIA**

All adult patients undergoing revascularisation surgery requiring a femoral approach who meet all the inclusion criteria and none of the exclusion criteria will be enrolled in this trial. Patients will be informed about the trial and will be invited to participate. All potential participants will be notified that the surgical procedure will be conducted per standard clinical practice. We will only randomise the type of skin closure (*i.e.*, intradermal sutures or metallic staples).

Patients can be enrolled in the trial if all of the following criteria apply:

1. Adult patients (≥ 18 years old)
2. Both genders
3. Diagnosed with chronic lower limb ischemia or aortic, iliac, or femoral aneurysm
4. With a scheduled surgery for one of the following indications:
 - a. Femoropopliteal bypass
 - b. Femorodistal bypass
 - c. Aortobifemoral bypass
 - d. Axillofemoral or axillobifemoral bypass

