Participants will be randomly assigned in a 1:1 ratio to intradermal suture (experimental group) or metallic staples (control group), using a computer-generated random sequence created with R version 4.1.0 (R Foundation for Statistical Computing, Vienna, Austria) for Windows® stratified by trial site. The randomization sequence was developed by a third-part statistician uninvolved with any other aspect of the trial. Patients will be randomized on the day of surgery prior to groin closure. The surgical team will remain unaware of the treatment assignment until subcutaneous tissue closure, when the nurse will disclose it and inform the team. Given the nature of the intervention, neither patients, surgeons, nor investigators will remain blinded to treatment allocation once it was undertaken. No masking technique will be performed. Data collection will be performed using an *ad hoc*-created electronic Case Report Form (eCFR) on the Research Electronic Data Capture (REDCap®) Platform, which generated an anonymized database. Each participant will be assigned a computer-generated code to ensure anonymity. Baseline data will include age, sex, body mass index, smoking history, past medical history (hypertension, diabetes, dyslipidemia, heart disease, stroke, chronic obstructive pulmonary disease, chronic kidney disease, human immunodeficiency virus [HIV]), blood-test results (plasma albumin, white blood cell count, hemoglobin, platelets, sodium, potassium, creatinine, glomerular filtration rate [GFR]), and surgical indication. For patients with a Rutherford ischemic stage 5 or 6, the infection status of any existing ulcer will be also documented based on the medical history. Additional data that will be collected include type of surgery, incision length, surgeon in charge of skin closure (staff vs. resident surgeon), prosthetic material type, operative time, number of days the patient was admitted to the hospital before the day of the surgery, and in-hospital stay. Operative time is defined as the time between the incision and the end of skin closure. The incision length will be gathered extending the edges of the incision after skin

closure.

Data will be securely stored with confidentiality protections in accordance with current local and European legislations on personal data protection. Independent monitoring will be performed throughout the study to ensure data accuracy, adherence to protocol, and to validate database entries against source documents.

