All analyses related to the intervention efficacy will be based on the intention-to-treat (ITT) population, reported according to CONSORT guidelines, basis (as reported in the CONSORT guidelines), keeping all patients selected and randomized in the group in which they were initially included, regardless of adherence to the protocol. Safety analyses will be based on the safety population who have been operated on after randomisation. The demographic and clinical profiles of all included subjects will be described by the study group using statistics according to variable type.

The primary outcome measure will be compared using the χ^2 test. The magnitude of the intervention effect will be presented as a cumulative incidence ratio (CIR) at 28 (± 2) days after surgery, along with a 95% confidence interval (95%CI). In the secondary outcomes, incidences will be compared using the χ^2 test and the magnitude of the effect will be presented as a CIR along with a 95%CI. A regression logistic model will be used to assess the effect of nutritional status, BMI, incision length, surgery duration, type of surgery, length of hospital before surgery, and femoral approach-related SSI up to 28 (± 2) days after surgery.

Analysis will be performed using R® version 4.1.0 for Windows® [R Core Team (2020). R: A language and environment for statistical computing. R Foundation for Statistical Computing, Vienna, Austria. URL: <https://www.Rproject.org/>].

INVESTIGATORS

Sponsor	[name] [name] Servicio de Angiología y Cirugía Vascular Hospital Universitario de Bellvitge [name] [name] [contact]
Principal Investigator	Dra. [name] Servicio de Angiología y Cirugía Vascular Hospital Universitario de Bellvitge [name] [name] [contact]
Coordinator	[name] Servicio de Angiología y Cirugía Vascular Hospital Universitario de Bellvitge [name] [name] [contact]
Investigators from other hospitals	Hospital Germans Trias: [name] [name] [contact] Trieste University Hospital: [name] [name] [contact]

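### Operative time includes the randomised skin closure and the risk-factor model does not list the arm, so the duration-SSI odds ratio can be biased downward, usually by little

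*Combined protocol and SAP*

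**What the plan says.** The Eligibility Criteria section limits randomisation to one step: "We will only randomise the type of skin closure". The section on randomisation, masking, data collection and monitoring then sets the end of the duration clock: "Operative time is defined as the time between the incision and the end of skin closure". It also says when the arm becomes known: "The surgical team will remain unaware of the treatment assignment until subcutaneous tissue closure, when the nurse will disclose it and inform the team".

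One secondary objective is "To assess the association between surgery duration and femoral approach-related SSI up to 28 (± 2) days after surgery". Statistical Methods addresses it with a single sentence that begins "A regression logistic model will be used to assess the effect of nutritional status, BMI, incision length, surgery duration, type of surgery" and goes on to pre-operative hospital stay. The study arm is not among the terms named.

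The Intervention Description contrasts staples placed 0.5 cm apart with a running intradermal stitch that alternates sides and ends in five knots, the last buried. No closure time is given for either technique. Under the Eligibility Criteria, both groins of a bilateral case receive the same closure and count as one intervention.

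**The concern.** An exposure that contains the randomised step carries information about the arm. Three conditions together produce bias: closure time differs by arm, the arm affects SSI, and the arm is left out of the model. The described techniques make the first plausible, the trial is powered on the second, and the listed terms leave the third open.

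If all three hold in the expected direction, slow operations are over-represented among sutured, lower-risk patients. A harmful effect of long surgery is then diluted, and no effect can look mildly protective. This is confounding by arm. Its direction is foreseeable, more patients do not shrink it, and the confidence interval does not show it. At stake is one secondary association objective.

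**Working it through.** **Plan figures.** The documents state nothing about operative or closure time, so there is no figure of theirs to reproduce on this point. The sample size supplies the inputs. For 9.2% against 25.0%, two-sided 5% and 80% power, the continuity-corrected formula gives 101 per group against the stated 100; 100/0.9 rounds up to 112 per group, 224 in total, as stated.

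**From the documents.** SSI risk is 0.092 (suture) and 0.25 (staples), with 1:1 allocation and 200 evaluable patients. The arm odds ratio is (0.092/0.908)/(0.25/0.75) = 0.304. Overall risk is 0.171, or 34.2 expected events.

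**Assumed, not in the documents.** Suturing takes Δ = 5, 10 or 20 minutes longer (20 might represent two groins). Pre-closure time is normal with SD 60 or 90 minutes. The true odds ratio is 1.00 or 1.10 per 30 minutes.

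**Step 1: bias under a true null, arm omitted.**
- P(suture | SSI) = 0.092/0.342 = 0.269.
- P(suture | no SSI) = 0.908/1.658 = 0.548.
- The difference is −0.2786, so mean measured time differs between cases and non-cases by −0.2786Δ minutes.
- The fitted log odds ratio per 30 minutes is close to 30 × (−0.2786Δ)/V. Here V = SD² + 0.239Δ², and 0.239 = 0.171 × 0.269 × 0.731 + 0.829 × 0.548 × 0.452.
- Example, Δ = 10 and SD 60: −83.6/3623.9 = −0.0231, an odds ratio of 0.977.

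A direct logistic fit to the expected outcomes gives the same null values to three decimals, and the following for a true 1.10:

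| SD (min) | Δ (min) | True 1.00 estimated as | True 1.10 estimated as |
|---|---|---|---|
| 60 | 5 | 0.989 | 1.082 |
| 60 | 10 | 0.977 | 1.070 |
| 60 | 20 | 0.956 | 1.044 |
| 90 | 5 | 0.995 | 1.089 |
| 90 | 10 | 0.990 | 1.083 |
| 90 | 20 | 0.980 | 1.072 |

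With the clock stopped before skin closure and the arm still omitted, the fits are 1.000 and about 1.095. The gap from 1.10 is non-collapsibility of the odds ratio, not confounding.

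**Step 2: size against sampling error.** The standard error of the log odds ratio per 30 minutes is about (30/SD)/√(200 × 0.171 × 0.829). That is 0.094 at SD 60 and 0.063 at SD 90. In standard errors, the null bias is:
- SD 60: 0.0116/0.094 = 0.12, 0.0231/0.094 = 0.25 and 0.0452/0.094 = 0.48.
- SD 90: 0.0052/0.063 = 0.08, 0.0103/0.063 = 0.16 and 0.0204/0.063 = 0.32.

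In 3,000 simulated trials of 100 per group, a true null was rejected about 6% of the time at SD 60 and Δ = 10. A harsher case outside this range (SD 30, Δ = 15) gave an odds ratio of about 0.77 per hour and about 10% rejection.

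**Step 3: the arm as a term.** Pre-closure time equals total time minus Δ for sutured patients. A model with both total time and arm therefore returns the true time odds ratio, 1.00 or 1.10, in every scenario. This is exact here because Δ is a constant shift. The arm odds ratio in that model becomes 0.304 × 1.10^(−Δ/30): 0.299 at 5 minutes and 0.285 at 20. It moves away from 0.304 because part of the closure step has been adjusted for.

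**The case against.** The strongest case against raising this is that it is small and conditional. Closure times are assumed. The arm effect comes from a retrospective study, the hypothesis is two-sided, and a smaller true effect gives a smaller bias. A true odds ratio of 1.10 per 30 minutes would have only about 17% power at SD 60 with no bias at all (0.0953/0.094 = 1.01 standard errors). The calculation also uses time alone, not the full list of covariates. All of this stands and limits the weight of the point.

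It is also fair that the model sentence is a loose list: it omits foot lesions, which are the subject of a stated objective. Silence about the arm is therefore not a decision to exclude it. Nor is skin-to-skin time a wrong definition; it is a legitimate reading of surgery duration. Both observations favour naming the arm over redefining the clock.

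A reader might infer that incision length has the same defect, since "The incision length will be gathered extending the edges of the incision after skin" closure and it too is a risk factor ("To assess the association between incision length and femoral approach-related SSI up to 28 (± 2) days after surgery"). The documents do not support that. The incision is cut before the team learns the arm, and nothing shows that either closure changes the length measured with the edges extended. At most there could be arm-related measurement error, for which no basis or figure is given.

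A reader might also infer that the treatment comparison is compromised. It is not: the primary analysis is an unadjusted χ² test with a cumulative incidence ratio and uses neither variable. No analysis adjusting the treatment effect for duration is planned.

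**Conclusion.** The point holds for operative time only, and as a possibility: the duration-SSI odds ratio can be biased downward if suturing is slower, suturing lowers SSI and the arm is not in the model. Over the assumed range, 1.10 per 30 minutes becomes about 1.04 to 1.09 and a null becomes about 0.96 to 0.99. That is 0.1 to 0.5 standard errors at 200 patients. It would be larger only if the closure-time difference were large relative to the spread of operative time. The documents do not establish that the bias is present, and they give no support for an arm effect on incision length. The point merits a change because the direction is foreseeable, a stated objective is affected and the remedy is almost free.

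**What to change.** In Statistical Methods, name the study arm as a term in the logistic model for SSI risk factors. State that the arm coefficient from that model is not an estimate of the treatment effect, which comes from the primary comparison. The arm is already recorded, so no data collection changes. The cost is one parameter against about 34 expected events and slightly lower precision: at SD 60 and Δ = 10, the standard error per hour rises from about 0.196 to 0.203.

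Alternatively, define the duration exposure for this objective as incision to the end of subcutaneous closure, when the nurse discloses the arm, and still report skin-to-skin time. That costs one extra clock reading per operation and works only for patients in whom it is taken.

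Measuring incision length before disclosure is an optional precaution, not a needed correction.

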Surgical site infections (SSI) are among the most common and fearsome complications in vascular surgery, given its high morbidity and mortality rates¹. SSI is associated with a two – to three-fold increased risk of death and a 60% increased risk of requiring postoperative intensive care support. It increases the length of hospital stay by 7-12 days, patients are five times more likely to require readmission, and direct healthcare costs raise at least US\$5000²⁻⁴. SSI is an infection that occurs after surgery in the part of the body where the surgery took place^{5,6}. It can be superficial, or deep, depending on its characteristics⁷. The groin is the most common infection site in vascular surgery, because it is a folding area with many lymph glands and is close to genitalia⁸. SSI incidence after vascular surgery has dropped from almost 30%⁹ in the 1980s to 20%¹⁰ in the 2000s and currently is approximately 10%¹¹. This reduction may be due to improvements in asepsis measures and operative time. A 2021 meta-analysis on strategies to prevent inguinal SSI reported that using intradermal sutures could associate a lower rate of SSI¹². One of the papers presents a retrospective SSI incidence analysis among 330 patients who underwent arterial vascular intervention through a groin incision. Intradermal suture closure was performed in 262 patients, of whom 24 (9.2%) presented SSI, while staples closure was conducted in the remaining 68, of whom 17 (25%) developed SSI¹³. Another paper, published in 2018, compared the infection rate before (2012-2015) and after (2015-2016) the implementation of a dedicated SSI prevention protocol, analyzing among other parameters, the inguinal closure technique (*i.e.*, intradermal suture Vs, metallic staples). The results were promising, as among the 18 patients with an SSI, 16 (89%) had metallic staples, and only 2 (11%) had intradermal sutures, being these results statistically significant¹⁴.

OBJECTIVES

- Our primary objective is to estimate the SSI incidence (superficial and/or deep) associated with a femoral approach up to 28 (± 2) days after surgery.
- Our secondary objectives are as follows:
 - To estimate the incidence of other surgical wound complications (e.g., seroma, hematoma, lymphorrhagia) up to 28 (± 2) days after surgery.
 - To estimate the incidence of sepsis in patients with SSI up to 28 (± 2) days after surgery.
 - To describe the timing of prophylactic antibiotic administration.

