Data will be anonymised and dissociated so that the corresponding patient cannot be identified. Patients will be assigned consecutive numbers as they are enrolled in the study, and these identification numbers (or codes) will be used in the eCRF; the full name of the patient will not be included in the eCRFs. The principal investigator of each center will keep an updated patient identification list containing the name, clinical history number, and the patient's identification number (or code) for the clinical trial. The study monitor may access the patient's identity and data related to the study monitoring procedures. Anyone with direct access to the data (Regulatory Authorities, Trial Monitors, and auditors) will take all possible precautions to maintain the confidentiality of patients' identities. It is the investigator's responsibility to obtain written informed consent from the study patients. The Trial Monitor's responsibility is to ensure that each patient has given their written consent to allow this direct access. The investigator shall ensure that the documents provided to the Sponsor do not contain the patient's name or any identifiable data.

STATISTICAL METHODS

Our primary endpoint is the number (percentage) of patients who present a femoral approach SSI up to 28 (± 2) days after surgery. We intend to contrast:

- Null hypothesis (H_0): there is no difference in the SSI incidence related to the femoral approach between the metallic stapling skin closure and the intradermal suture skin closure.
- Alternative hypothesis (H_1): the SSI incidence related to the femoral approach when performing a metallic stapling closure differs from the incidence when performing an intradermal suture skin closure.

To our knowledge, no published prospective studies compare SSI incidence between staples and intradermal closure. Nonetheless, a 2018 retrospective Finnish study estimated an SSI incidence of 9.2% for intradermal suture skin closure and 25.0% for metallic stapling skin closure¹³. Under this assumption, 200 patients (100 per study group) would be necessary to reject the null hypothesis at a 5% significance level and a power of 80% using a two-sided χ^2 test with a 1:1 allocation to treatment groups. Accounting a possible dropout rate of 10%, 224 subjects should be enrolled (112 per study group).

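### Randomisation is stratified by site but the primary χ² test and CIR ignore site; a site-stratified analysis would be a small, cheap gain, not the repair of an error

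*Combined protocol and SAP*

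**What the plan says.** Under Randomization, Masking, Data Collection and Monitoring, allocation is 1:1 and "stratified by trial site". No block size is mentioned. The Study Setting section gives the strata: "It will be performed in the Bellvitge University Hospital, Germans Trias i Pujol University Hospital, and Trieste University Hospital".

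Under Statistical Methods, "The primary outcome measure will be compared using the χ^2 test", and the effect is reported as a CIR at 28 days with a 95% confidence interval. Neither is described as stratified or adjusted. The only regression in the plan is for risk factors: "A regression logistic model will be used to assess the effect of nutritional status, BMI, incision length, surgery duration, type of surgery", followed by length of hospital stay before surgery. Site is not in that list. No stated analysis therefore uses the one factor on which randomisation was stratified.

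The sample size, also under Statistical Methods, was obtained "using a two-sided χ^2 test with a 1:1 allocation to treatment groups". Sizing and planned analysis thus agree with each other.

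**The concern.** When randomisation is stratified by a factor that predicts the outcome, the usual practice is to carry that factor into the analysis. An unstratified test leaves differences between hospitals in the error term. If arms are balanced within site, the test statistic then varies less under the null than its reference distribution assumes, so the test becomes conservative and its interval slightly too wide. If allocation is not balanced within site, the test keeps its level and loses only power and precision.

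Either way the possible cost is some power and precision on the trial's single confirmatory comparison. It arises only if infection rates really differ between the three hospitals, and the documents contain nothing on that.

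**Working it through.** **Inputs from the protocol (Statistical Methods).** Infection rates 25.0% (staples) and 9.2% (intradermal); two-sided 5% level; 80% power; 100 per group before dropout; 224 after 10% dropout.

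**The plan's own figure.** With mean rate (0.25 + 0.092)/2 = 0.171 and difference 0.158:

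n = [1.960·√(2 × 0.171 × 0.829) + 0.842·√(0.25 × 0.75 + 0.092 × 0.908)]² / 0.158² = 87.95, so 88 per group (176 in total) without continuity correction.

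With the correction: (87.95/4) × [1 + √(1 + 4/(87.95 × 0.158))]² = 100.2, which is 101 per group rounded up (202 in total), against the stated 100 (200). Dropout: 100/0.9 = 111.1, so 112 per group and 224 in total, as stated. The planned N therefore fits the continuity-corrected test, although the plan does not say which version will be used.

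**Assumptions for the comparison.** These are not in the documents: 200 analysed; sites of 100, 60 and 40; a common odds ratio between arms; overall rates held at 25.0% and 9.2%. Four patterns of staple-arm rate by site were used: alike (25/25/25%), mild (20/28/33%), threefold (15/28/45%) and 5.5-fold (10/30/55%). Arms were either exactly balanced within site or allocated by independent 1:1 draws (unblocked). There were 400,000 simulated trials per scenario, with Monte Carlo standard error at most 0.06 points for power and 0.04 for type I error.

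**Power (%), plain χ² / CMH.** Changes quoted elsewhere were taken before rounding.

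| Sites | Uncorrected, balanced | Uncorrected, unblocked | Corrected, balanced | Corrected, unblocked |
|---|---|---|---|---|
| Alike | 86.3 / 86.1 | 85.9 / 85.4 | 80.8 / 81.0 | 80.8 / 80.3 |
| Mild | 86.4 / 86.4 | 86.0 / 85.8 | 80.9 / 81.4 | 81.0 / 80.8 |
| Threefold | 86.8 / 87.7 | 85.9 / 87.1 | 81.4 / 83.0 | 80.8 / 82.3 |
| 5.5-fold | 87.8 / 89.9 | 86.0 / 89.5 | 82.3 / 85.7 | 80.9 / 85.0 |

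**Type I error (%) of the uncorrected χ², arms balanced within site.** The three common rates are the current incidence in the introduction, the mean of the two assumed rates, and the assumed staple rate.

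| Common rate | Alike | Mild | Threefold | 5.5-fold |
|---|---|---|---|---|
| 10% | 5.2 | 5.1 | 4.8 | 4.3 |
| 17.1% | 5.1 | 5.0 | 4.5 | 3.7 |
| 25% | 4.9 | 4.8 | 4.1 | 3.2 |

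CMH gives 4.9 to 5.2% in all of these. With unblocked allocation the plain χ² stays at 5.0 to 5.1% throughout.

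**Hand check of the last row.** With exact balance, the true variance of the crude difference is the fraction k = Σw·p(1−p) / [p̄(1−p̄)] of what the plain χ² assumes, where w is the site share (0.5, 0.3, 0.2). For 10/30/55%: 0.5 × 0.09 + 0.3 × 0.21 + 0.2 × 0.2475 = 0.1575, and k = 0.1575/0.1875 = 0.84. The effective critical value is 1.960/√0.84 = 2.138, which gives a two-sided error of 3.2%, as simulated.

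**Interval width.** The mean ratio of Mantel-Haenszel to crude standard error of log CIR, from alike to 5.5-fold, is 1.000, 0.996, 0.979 and 0.952 balanced, and 1.006, 1.002, 0.986 and 0.959 unblocked. With equal arms within site the CIR point estimate itself does not change.

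**Sensitivity.** With sites of 140, 40 and 20 and similarly graded site differences, the uncorrected power changes are −0.2, 0.0, +0.7 and +2.4 points balanced, and −0.5, −0.3, +0.9 and +3.6 unblocked. A separate set of scenarios, with equal sites or sites of 120, 60 and 20, gave about −0.6 to +1.5 points uncorrected, and 4 to 6 points only in one extreme case (staple rates 10/32.5/92.5%).

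**The case against.** The strongest reply is that an unadjusted 2×2 test after stratified allocation is a legitimate plan and no conclusion becomes unreliable under it. That is right, and it is why this is an improvement and not an error.

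The benefit also rests on site differences that nothing in the protocol supports. All three hospitals are described as specialised centres, eligibility is common to them, emergencies and previously operated groins are excluded, and preparation and deep closure follow one description. This does not show that rates are equal, but it makes the alike and mild patterns at least as natural a starting point, and there the stratified test gains essentially nothing.

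The conservatism figures need both balance within site and an uncorrected χ². The plan mentions no blocks, and its N fits the corrected test. They describe one possible configuration and should not be read as expected behaviour.

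Two further points stand as conditions on the remedy. The trial is open-label, so changing the primary test is clean only if it is fixed before outcome data are examined. And because the sample-size text names the χ², replacing the test calls for a matching edit there. Finally, the unstated continuity correction moves power by about 5 points (86% against 81%), more than site stratification does in any of the four main patterns.

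What remains is an uneven trade: about half a point of power at risk with uncorrected tests, against roughly 1 to 3.5 points if hospitals differ strongly, using a variable known for every randomised patient.

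**Conclusion.** The point holds, as a minor one. Site governs the randomisation and appears in no planned analysis, yet the plain χ² and crude CIR are valid: no inflation of type I error beyond simulation and discreteness effects (at most 5.2%), and power of at least 80.8% at the assumed rates, corrected or not. Stratifying by site costs at most about 0.5 points of power with uncorrected tests in the main scenarios if sites are alike. It gains about 1 point if staple-arm rates differ threefold and 2 to 3.5 points if they differ 5.5-fold. The Mantel-Haenszel interval is then about 1 to 5% narrower on the log scale.

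All of this depends on assumed site sizes, assumed site rates, a common odds ratio, and an allocation method that the plan does not fully describe.

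**What to change.** Prespecify a site-stratified CMH test as the primary test, with a site-stratified Mantel-Haenszel CIR and 95% confidence interval, and keep the crude χ² and CIR as supporting results. State in the same sentence whether a continuity correction applies, and apply the same choice to both tests. If the sponsor prefers to keep the χ² as primary, so that it continues to match the sizing text, add the stratified test and CIR as a prespecified sensitivity analysis.

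Whichever option is taken, date it before outcome data are examined.

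The cost is one or two sentences under Statistical Methods, plus a consequential word in the sample-size paragraph if the primary test changes. No new data are needed and the enrolment target remains 224.

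### No planned analysis adjusts the treatment effect for site or baseline SSI risk factors; a pre-specified adjusted CIR beside the χ² test would be a modest, cheap improvement

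*Combined protocol and SAP*

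**What the plan says.** The STATISTICAL METHODS section of the combined protocol and SAP gives the whole primary analysis in two sentences: "The primary outcome measure will be compared using the χ^2 test", and "The magnitude of the intervention effect will be presented as a cumulative incidence ratio (CIR) at 28 (± 2) days after surgery", with a 95% confidence interval. It mentions no covariate and no stratification factor, and no adjusted treatment effect appears even as a sensitivity analysis.

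Four other places bear on this:

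- **Randomisation section.** Allocation is 1:1 and stratified by trial site only. "Baseline data will include age, sex, body mass index, smoking history, past medical history", and the history list that follows includes diabetes. The same section refers to patients at Rutherford stage 5 or 6.
- **OBJECTIVES.** A secondary objective is "To assess the association between Body Mass Index (BMI) and femoral approach-related SSI up to 28 (± 2) days after surgery". A parallel objective covers foot lesions at Rutherford 5 or 6. Diabetes is not named as a possible SSI determinant.
- **OUTCOMES.** BMI and presence of foot lesions are listed among the secondary measures.
- **STATISTICAL METHODS, logistic model.** One regression is planned, for nutritional status, BMI, incision length, surgery duration, type of surgery and preoperative stay. It lists no arm term, site, Rutherford stage or diabetes.

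**The concern.** With about 100 evaluable patients per arm, the arms can differ by chance in patient-level risk, and an unadjusted CIR carries that difference into the answer. Stratifying by site does not balance BMI, foot lesions or diabetes. The site factor is itself dropped at the analysis stage.

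The existing logistic model does not fill the gap. It has no arm term, so it does not estimate a treatment effect. Adding one would not be enough, because surgery duration is timed to the end of skin closure and incision length is measured after closure. Neither is a baseline variable, and duration includes the time taken by the randomised closure itself.

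Two things are at stake: a little precision, and credibility. The trial is open-label. If an imbalance appears in the baseline table, any adjustment chosen then will be post hoc and open to challenge.

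**Working it through.** **1. The plan's sample size.** Inputs from STATISTICAL METHODS: the cited study "estimated an SSI incidence of 9.2% for intradermal suture skin closure and 25.0% for metallic stapling skin closure"; "at a 5% significance level and a power of 80% using a two-sided χ^2 test with a 1:1 allocation to treatment groups"; and "200 patients (100 per study group) would be necessary to reject the null hypothesis".

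- Difference 0.250 − 0.092 = 0.158; mean rate (0.250 + 0.092)/2 = 0.171.
- Uncorrected: n = [1.96·√(2·0.171·0.829) + 0.842·√(0.25·0.75 + 0.092·0.908)]² / 0.158² ≈ 88 per arm.
- With continuity correction: (88/4)·[1 + √(1 + 4/(88·0.158))]² ≈ 100.2, or 101 rounded up. This reproduces the stated 100.
- Dropout: 100/0.9 = 111.1, rounded up to 112 per arm, 224 in total. This also agrees.
- Power of the uncorrected χ² test at 100 per arm: Φ[(0.158·√100 − 1.96·√(2·0.171·0.829)) / √(0.25·0.75 + 0.092·0.908)] = Φ(1.03) ≈ 84.9%; at 112 per arm, 88.6%.

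The planned 80% therefore does not depend on adjustment.

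**2. Events available.** At the design rates: 25 + 9.2 = 34.2. At the roughly 10% current incidence given in the introduction: 200 × 0.10 = 20. Arm, two site terms, BMI and Rutherford 5-6 make five parameters, and diabetes makes six.

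| Events | Per parameter, 5 terms | Per parameter, 6 terms |
|---|---|---|
| 34.2 | 6.8 | 5.7 |
| 20 | 4.0 | 3.3 |

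**3. How far chance imbalance can move the answer.** Assume a factor with 35% prevalence (not in the documents). The 95% range of the between-arm gap is ±1.96·√(2·0.35·0.65/100) = ±13.2 points. Hold the overall SSI risk at 17.1%:

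- Odds ratio 2: risks 13.5% without and 23.8% with the factor. Shift = 0.132 × 10.3 ≈ 1.4 points.
- Odds ratio 3: risks 11.4% and 27.8%. Shift = 0.132 × 16.4 ≈ 2.2 points.

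The planned difference is 15.8 points. When several factors lean the same way the shift is larger. With assumed odds ratios of 1.5 per SD of BMI, 2 for diabetes and 2 for Rutherford 5-6, take the tenth of simulated trials in which prognosis most disfavours the suture arm. There the mean difference is about 13.4 points unadjusted and 15.5 adjusted (site omitted, diabetes 45%, Rutherford 5-6 35%).

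**4. Average gain on the plan's own scale.** Simulation at 25% vs 9.2%, 100 per arm. The model had arm, site, BMI, diabetes and Rutherford 5-6, and was standardised to a CIR. All predictor strengths are assumptions.

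| Assumed strength (BMI per SD / diabetes / Rutherford 5-6) | Variance of log CIR, adjusted ÷ unadjusted |
|---|---|
| Weak (1.3 / 1.5 / 1.5) | about 1.01 |
| Moderate (1.5 / 2 / 2) | about 0.98 |
| Stronger (1.7 / 2.5 / 2.5) | about 0.96 |

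Allowing for simulation error, that is a reduction of nil (weak) to about 2-5% (moderate to stronger). Since √0.98 = 0.99 and √0.95 ≈ 0.975, the interval on the log scale narrows by about 1 to 2.5%. Power rises by 0 to 3 points over the unadjusted CIR test. Type I error was about 4-5%. At a 10% SSI rate with a small low-risk site, the fit failed in up to about 10% of trials.

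**The case against.** The case for leaving the plan alone is strong on several counts:

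- **Validity.** Randomisation makes the unadjusted test valid, and its type I error already allows for chance imbalance. It is also the test that sized the trial. This stands, and it is why the χ² test should remain primary.
- **Strength of predictors.** A reader might infer that the trial ignores strong, known predictors. The documents do not support that. BMI and foot lesions are posed as associations to be assessed, diabetes is never linked to SSI, and no effect sizes are given.
- **Role of the logistic model.** A reader might also assume that the plan already uses all three variables in its risk-factor model. It lists only BMI.
- **Size and cost.** The average gain may be nil, and with weak predictors there can be a slight loss. With 20-34 events, a five- or six-parameter model is less stable than a two-by-two table. This stands, and it argues for few covariates and a written fallback.
- **Visibility.** Baseline profiles will be described by arm, so an imbalance would be seen. But seeing it gives no pre-agreed way to deal with it.

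The worry that the adjusted analysis inflates type I error does not hold on the log-CIR scale, where it was about 4-5%.

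**Conclusion.** The point holds as an improvement in robustness and, to a small degree, efficiency. It is not a flaw that invalidates the primary analysis. No planned analysis adjusts the treatment effect for the stratification factor or for baseline risk factors the trial already collects. The omission of site is the better-documented part, because it follows from the trial's own randomisation.

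The average benefit is small, as the working shows. The main benefit is a pre-agreed estimate if the arms turn out to be imbalanced. Because the χ² test stays primary, the power of the primary test is unchanged.

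The size rests on assumed odds ratios, assumed prevalences and the design event rates. It would not be right to conclude that the χ² result is biased, that the trial is underpowered without adjustment, or that the primary test must be replaced.

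**What to change.** In STATISTICAL METHODS, keep the χ² test as the primary test and the unadjusted CIR as its companion. Add one paragraph that pre-specifies:

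- **Estimate:** a CIR with 95% CI, standardised from a logistic model with arm, site, BMI (continuous) and Rutherford 5-6 (yes/no). Diabetes is an optional third covariate, to be decided now.
- **Coding:** aneurysm patients are eligible and may have no Rutherford stage. Code those without foot lesions as no.
- **Exclusions:** no variable fixed after randomisation, in particular surgery duration and incision length.
- **Fallback:** if the model does not converge, drop the site terms. If it still fails, report the unadjusted CIR.

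The cost is a paragraph of text and a few lines of R, with no extra patients, visits or data items. The constraint is that the covariates must be fixed before outcome data by arm are seen, and kept to these few.
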